5.6.3.2 All TEAEs

The following summaries will be provided for all TEAEs:

- TEAEs by SOC and PT
- TEAEs by decreasing frequency of PT
- Most common (eg, $\geq 10\%$) TEAEs by SOC and PT
- TEAEs by SOC, PT, and worst toxicity grade

5.6.3.3 Intolerable Grade 2 and \geq Grade 3 TEAEs

The intolerable Grade 2 and \geq Grade 3 TEAEs will be summarized by SOC and PT.

In addition, a listing of intolerable Grade 2 and \geq Grade 3 AEs will be provided.

5.6.3.4 Treatment-related TEAEs

The following treatment-related TEAEs will be summarized:

- Treatment-related TEAEs by SOC, PT and worst toxicity grade
- Most common (eg, $\geq 10\%$) treatment-related TEAEs by SOC and PT

5.6.3.5 Serious TEAEs

The incidence of serious TEAEs will be summarized as below:

- Serious TEAEs by SOC and PT
- Treatment-related serious TEAEs by SOC and PT
- Serious TEAEs by decreasing frequency of PT
- Most commonly reported (eg, $\geq 5\%$) serious TEAEs by SOC and PT
- Serious TEAEs adjusted by treatment duration

In addition, a listing of serious AEs will be provided.

5.6.3.6 TEAEs Leading to Treatment Discontinuation

The proportion of subjects who discontinued treatment due to toxicity and time to treatment discontinuation due to toxicity will be summarized descriptively.

The TEAEs leading to treatment discontinuation (discontinuation of both study drugs in each treatment arm) will be summarized by SOC and PT for those subjects indicated as having discontinued study treatment due to an adverse event on the CRF treatment disposition page.

The TEAEs leading to study drug discontinuation for each individual drug will also be summarized.

A listing of AEs leading to treatment discontinuation or any study drug discontinuation will be provided.

5.6.3.7 TEAEs Leading to Dose Reductions and Dose Interruptions

The TEAEs leading to dose reductions and dose interruptions will be summarized by SOC and PT for each treatment arm. The TEAEs leading to dose reductions and dose interruptions will be summarized for each individual drug and overall.

A listing of AEs leading to dose reductions and/or dose interruptions of any study drug will be provided.

5.6.3.8 Grade 3 or Higher TEAEs

The following Grade 3 or higher TEAEs will be summarized:

- Grade 3 or higher TEAEs by SOC and PT
- Most commonly reported (eg, $\geq 5\%$) Grade 3 or higher TEAEs by SOC and PT
- Grade 3 or higher TEAEs leading to treatment discontinuations, dose reductions and/or dose interruptions by SOC and PT

In addition, a listing of Grade 3 or higher AEs will be provided.

5.6.3.9 TEAEs with Fatal Outcome

The TEAEs with fatal outcome will be summarized by SOC and PT for each treatment arm. Treatment-related TEAEs with fatal outcome will also be summarized.

A listing of AEs with fatal outcome will be provided.

5.6.3.10 Deaths

The number of subjects who died during the study will be summarized.

A listing of subjects who died during the study will be provided.

5.6.3.11 Adverse Events of Clinical Interest

Clinically significant adverse events (CSAEs) for lenvatinib and treatment-emergent AEs of special interest (AEoSI) for everolimus will be identified based on a thorough review of safety data from the clinical and pharmacovigilance database.

Evaluations of the CSAEs and AEoSI will be based on standardized MedDRA queries (SMQs), customized MedDRA queries (CMQ), or sponsor-generated queries (SGQs), which included sponsor-specified PT either alone or in addition to those listed for an SMQ or CMQ.

CSAEs and AEoSI will be summarized by overall, CTCAE grade and treatment cycle. The subjects with CSAEs and AEoSI leading to dose reductions, dose interruptions, and treatment discontinuations will also be provided.

In addition, number of subject with hypertension leading to administration of concomitant medication and type of antihypertensive medication received will be summarized. Time to first onset of hypertension (defined as the time from the date of first dose date to the date of first onset of hypertension) will also be summarized. Similar analysis will also be provided for the subjects who had proteinuria.

Hypertension based on vital sign data will also be summarized. Details are specified in the vital sign [Section 5.6.5](#).

Proteinuria based on urine dipstick data will also be summarized. Details are specified in the urinalysis [Section 5.6.4.2](#).

5.6.4 Laboratory Values

Laboratory results will be summarized using Système International (SI) units. Laboratory values that are non-missing and reported as ‘below the detectable limit’ of an assay will be replaced by half the detectable limit in the summary tables. Central laboratory test results will be used as the primary data source for laboratory analyses. Only when the central laboratory tests results are missing, the local laboratory test results will be used as substitute.

On-treatment laboratory tests will be defined as the laboratory tests conducted from the start of treatment to no more than 28 days after the last dose of study treatment.

5.6.4.1 Hematology and Clinical Chemistry

Laboratory parameters will be graded based on CTCAE Version 4.03. In the summary of laboratory parameters by CTCAE grade, for parameters with CTCAE grading in both high and low direction (eg, calcium, glucose, magnesium, potassium, sodium), CTCAE grades in both high and low directions will be summarized separately.

The evaluation of clinical laboratory tests will focus on the following selected laboratory analytes:

Hematology Panel:

- hematocrit, hemoglobin, red blood cell (RBC) counts, white blood cell (WBC) count, absolute neutrophil count, and absolute lymphocyte count, platelet count

Chemistry Panel:

- Electrolytes: bicarbonate, calcium, chloride, magnesium, phosphate, potassium, sodium
- Liver function tests: alanine aminotransferase (ALT), alkaline phosphatase, aspartate aminotransferase (AST), direct bilirubin, total bilirubin
- Renal function tests: blood urea/blood urea nitrogen (BUN), creatinine
- Thyroid function tests: thyroid stimulating hormone (TSH), free T4 level
- Other: albumin, cholesterol, triglycerides, glucose, calcium, lactate dehydrogenase (LDH), amylase, lipase, creatine kinase

Descriptive statistics for values and changes from baseline at each scheduled visit for hematology and chemistry laboratory parameters will be provided. Box plots of laboratory values over time will also be provided for selected hematology and chemistry parameters.

In addition, the worst CTCAE grade in hematology and chemistry during the treatment will be summarized by treatment arm and CTCAE grade. Shift tables from baseline to the worst CTCAE grade during treatment will be generated.

Subjects with treatment-emergent markedly abnormal values (TEMAV) will be summarized. Treatment-emergent markedly abnormal value is defined as a value that is outside of the normal range and the CTCAE grade increased from baseline by 2 or more grades, except for phosphate which must have shifted by 3 or more grades.

5.6.4.2 Urinalysis

Proteinuria: Shifts from baseline to worst postbaseline for proteinuria determined by dipstick (negative, trace, 1+, 2+, 3+, 4+) will be presented by treatment arm.

The urinalysis results from 24-hour urine protein will also be summarized by worst Grade.

5.6.5 Vital Signs

Descriptive statistics for vital sign parameters (systolic and diastolic blood pressure, pulse, respiratory rate, temperature, and weight) and changes from baseline at each scheduled visit will be presented.

Blood pressure will also be summarized using a shift table from baseline to worst postbaseline CTCAE grade by the categories defined in [Table 8](#) below based on CTCAE grades.

Table 8 Blood Pressure Grades

Grade	Blood Pressure (mm Hg)	
	Systolic	Diastolic
0 (Normal)	≤119	≤79
1 (Prehypertension)	120–139	80–89
2 (Stage 1 Hypertension)	140–159	90–99
3 (Stage 2 Hypertension)	≥160	≥100

Subjects with systolic blood pressure ≥ 140 mm Hg or diastolic blood pressure ≥ 90 mm Hg during treatment will be listed along with their hypertensive medications.

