- e. Assessments will include vital signs (resting BP [including date and time of measurement], HR, RR and body temperature), weight, and height. Height will be measured at the Screening visit only. One BP assessment is defined as the mean value of 3 measurements at least 5 minutes apart. An elevated BP assessment (ie, systolic BP ≥140 mmHg or diastolic BP ≥90 mmHg) should be confirmed by a repeat assessment after a minimum of 1 hour. Subjects with systolic BP ≥160 mmHg or diastolic BP ≥100 mmHg must have their BP monitored every 2 weeks (on Day 1 and Day 15 or more frequently, as clinically indicated) until systolic BP has been ≤150 mmHg and diastolic BP has been ≤95 mmHg for 3 consecutive months. A diary will be provided to the subject to capture the blood pressure evaluations between study visits. See subsection for [management of hypertensive subjects](#).
Note: During Cycle 3 and subsequent cycles, subjects may return to the clinic for the Day 15 visit if BP monitoring testing is required as specified above. The Day-15 visit is mandatory in Cycles 1 and 2.
- f. A comprehensive physical examination (including a neurological examination) will be performed at the Screening or Baseline Visits, on Cycle 1/Day 15, on Day 1 of each subsequent cycle, and at the Off-Treatment assessment. A symptom-directed physical examination will be performed on C1D1

and at any time during the study, as clinically indicated.

- g. Required if screening physical examination was performed >7 days prior to C1D1.
- h. Single 12-lead ECG. Subjects are suggested to be in the recumbent position for a period of 5 minutes prior to obtaining ECG.
- i. An echocardiogram or MUGA scan to assess LVEF will be performed at Screening and as clinically indicated.
- j. A serum or urine pregnancy test will be performed at the Screening Visit, at the Baseline Visit (or within 72 hours prior to the first dose of study drug), at Day 1 of every cycle (starting with Cycle 2), and at the Off-Treatment assessment in women of childbearing potential (ie, premenopausal and perimenopausal women who have been amenorrheic for less than 12 months).

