- k. Clinical chemistry and hematology results must be reviewed prior to administration of study drug on C1D1 and within 2 business days of receipt of results for all subsequent cycles. Electrolytes such as potassium, calcium, and magnesium should be monitored and abnormalities should be corrected in all subjects before starting treatment per the Investigator's discretion. Clinical laboratory assessments may be conducted anytime within 72 hours prior to the scheduled visit, unless otherwise specified. If there is \geq Grade 3 hematologic or clinical chemistry toxicity, repeat the specific laboratory test and AE assessment at least 3-7 days (until improvement to <Grade 3). For subjects with blood glucose >ULN, a fasting (>6 h, water only) blood glucose sample will be obtained.
- l. Urine dipstick testing for subjects with proteinuria $\geq 2+$ should be performed locally every 2 weeks (on Day 1 and Day 15 or more frequently as clinically indicated) until the results have been 1+ or negative for 3 consecutive months. Urine dipstick testing should be performed preferably at the investigational site (but may be performed locally by the primary care physician or a local laboratory if the subject does not have to come for a visit to the site). If a new event of proteinuria $\geq 2+$ occurs, the subject must resume the Day-15 urine dipstick testing for evaluation of proteinuria until results are 1+ or negative for 3 consecutive months. For subjects with a history of dipstick proteinuria $\geq 2+$, see subsection for [management of proteinuria](#).

Note: During Cycle 3 and subsequent cycles, subjects may return to the clinic for the Day-15 visit if urine dipstick testing is required as specified above. The Day-15 visit is mandatory in Cycles 1 and 2.

- m. Blood samples for PK profiling of lenvatinib and everolimus will be drawn at 0.5-4 h and 6-10 h postdose on C1D1; predose and 0.5-4 h and 6-10 h postdose on C1D15, and predose and 2-12 h postdose on C2D1. If possible, a blood sample for the measurement of the concentration of lenvatinib should be drawn at the first report of an SAE or a severe unexpected AE. A blood sample to measure study drug plasma concentrations will no longer be needed after the data cutoff for the primary analysis.

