9.7.1.8.4 VITAL SIGNS

Descriptive statistics for vital signs parameters (ie, systolic and diastolic BP, pulse, respiratory rate, temperature, and weight) and changes from baseline will be presented by visit and treatment group. Subjects will be included in the summary if they had both a Baseline value and at least 1 postbaseline value.

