5 STATISTICAL METHODS

In general, continuous variables will be summarized using descriptive statistics such as mean, standard deviation (SD), median, and range (minimum and maximum). Categorical variables will be summarized using frequency and percentage. For time-to-event variables, which is defined as the time from the date of randomization to the date of the event, the Kaplan-Meier method will be used for descriptive summaries. For the calculation of time-to-event or duration-of-event variables for on-study events, the difference between the start date and the end date plus 1 day will be used. For durations of events (eg, baseline disease characteristics or prior therapies) prior to randomization, the durations will be calculated as the date of randomization minus the date of the event, the details are specified in [Section 8.4.1](#).

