8 DEFINITIONS AND CONVENTIONS FOR DATA HANDLING

8.1 Visit Windows

Visit windows will be defined to be upper and lower bounds of 3 days of the scheduled visit, following the protocol, which states that efforts should be made to conduct study visits (and safety assessments) on the day scheduled (± 3 days).

Tumor assessments are to be performed every 8 weeks (during the 8th week, starting from the date of randomization), or sooner if clinically indicated, until progressive disease during Randomization Phase. If a subject discontinues from study treatment without disease progression, tumor assessments should continue to be performed every 8 weeks until documentation of disease progression or beginning a new anticancer treatment during Follow-up Period.

In the calculation of descriptive statistics for laboratory values and vital signs, if a visit has multiple observations, the observation closest in date and time to the target visit day will be used in the analysis. If two or more observations have the same distance to the target visit day, the one that has the highest CTCAE grade or is furthest away from the normal range will be used.

The purpose of this windowing is to provide a single record per subject per visit for the calculation of descriptive statistics per scheduled visit, and change from baseline per visit. Other safety analyses (eg, worst grade laboratory results and shift tables) will include all postbaseline assessments, including those scheduled and unscheduled visits.

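### From Cycle 3 the Day-15 vital-sign rows describe only subjects recalled for earlier high blood pressure or proteinuria, so they are not comparable with the other by-visit rows or between arms as randomized groups

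*SAP*

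**What the plan says.** **Schedule.** In protocol Table 6 (section 9.5.2), Day 15 of Cycle 3 onward has its own column of numbered visits (8, 10, 12, 14 and so on). Vital signs are marked there. Physical examination, chemistry/hematology and dipstick are blank.

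**Who attends.** Footnotes e and l both state: "The Day-15 visit is mandatory in Cycles 1 and 2". After that, footnote e says "subjects may return to the clinic for the Day 15 visit if BP monitoring testing is required as specified above". The trigger is systolic pressure of at least 160 or diastolic of at least 100 mmHg. Footnote l adds a second route: "subjects may return to the clinic for the Day-15 visit if urine dipstick testing is required as specified above", which follows dipstick proteinuria of 2+ or more.

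**What is tabulated.** SAP 5.6.5 covers systolic and diastolic pressure, pulse, respiratory rate, temperature and weight; values "and changes from baseline at each scheduled visit will be presented". SAP section 5 sets the statistics: "continuous variables will be summarized using descriptive statistics such as mean", with SD, median and range. Protocol 9.7.1.8.4 matches: "changes from baseline will be presented by visit and treatment group". It restricts the summary only to subjects with a baseline and at least one later value. The windowing rule in SAP 8.1 exists to "provide a single record per subject per visit for the calculation of descriptive statistics per scheduled visit". None of these sections drops, separates or flags the conditional Day-15 visits.

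**The concern.** A table built as the SAP is written will alternate two kinds of row from Cycle 3. Day-1 rows cover everyone still on treatment. Day-15 rows cover those recalled because of a toxicity seen after randomization. A reader will naturally take the rows as one time course and compare the arms at each step, and neither reading is sound. If the arms differ in how many subjects are recalled, or why, the Day-15 contrast is not between randomized groups, and an arm with less hypertension could show equal or higher pressure among its few attenders.

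The trial asks whether the 14-mg start is safer. Protocol 9.4.2.2 treats hypertension as a recognized effect of this drug class, and the affected cycles come after the 14-mg arm's planned escalation at the start of Cycle 2. All the other vital signs share the same selected denominator.

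**Working it through.** The documents give no blood-pressure mean, SD or attendance count, so there is no plan figure to reproduce. The check has two parts.

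**1. The sections side by side**

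| Visit | Who is expected (Table 6, footnotes e and l) | In the SAP 5.6.5 by-visit summary? |
|---|---|---|
| Day 15, Cycles 1 and 2 | all on treatment | yes |
| Day 1, every cycle | all on treatment | yes |
| Day 15, Cycle 3 onward | only those under BP or dipstick monitoring | yes, no exception stated |

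Attendance is also partly discretionary: the footnotes say these subjects may return, a diary captures readings between visits, and dipsticks may be done elsewhere.

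**2. Direction and size**

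Quantity: D = mean(Y among attenders) - mean(Y among all on treatment), where Y is Day-15 systolic pressure from Cycle 3. All inputs below are assumptions.

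*Simplest model.* Select on a Day-1 reading of at least 160 in the same cycle, with no treatment and no proteinuria route. Then D = rho x SD x h(z), where z = (160 - mean)/SD and h is the normal density divided by the upper-tail probability.
- Mean 130, SD 15, rho 0.5: z = 2, h = 2.373, D = 0.5 x 15 x 2.373 = 17.8 mmHg.
- Simulated pairs: 147.7 v 130; 150.8 v 135; 157.3 v 135; 156.8 v 140. D is about 16 to 22 mmHg.

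*Fuller model.* Protocol 9.4.2.2 puts treatment between the trigger and the later reading, and monitoring continues after control. Inputs:
- true baseline systolic mean 130, between-subject SD 12, within-visit SD 10; entry requires a baseline reading of 150 or less;
- on-treatment rise of mean 8, SD 6;
- trigger at 160; exit after readings of 150 or less for 2 or 3 cycles;
- antihypertensive effect of 0, 10, 20 or 30 mmHg after the trigger;
- 0, 10 or 20% of subjects returning for proteinuria irrespective of pressure.

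Results, averaged over Cycle 3 to 9 Day-15 visits (range over exit rule and proteinuria share):

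| Antihypertensive effect | Share attending | D, mmHg | Mean change from baseline: attenders / all |
|---|---|---|---|
| 0 | 20 to 38% | +6.9 to +15.6 | +11.9 to +15.2 / +9.2 |
| 10 | 12 to 33% | +2.8 to +9.4 | +5.6 to +6.4 / +6.7 to +6.9 |
| 20 | 7 to 29% | -0.5 to +0.1 | -4.8 to +1.9 / +4.2 to +4.4 |
| 30 | 5 to 27% | -10.4 to -2.5 | -16.4 to -2.2 / +1.7 to +1.9 |

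Examples: with no effect, 151.7 - 136.1 = +15.6; with 30 mmHg, 118.4 - 128.8 = -10.4.

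Two readings follow.
- With a 10 mmHg effect, attenders sit above everyone on level but slightly below on change from baseline, so two columns of one table point in opposite directions.
- Take the 10 mmHg effect and the 3-cycle exit. Attenders average 142.0 with no proteinuria route and 136.8 when 20% return for proteinuria, a gap of 142.0 - 136.8 = 5.2 mmHg. The all-subject means are 133.7 and 133.6. Two arms that differ only in why subjects return would show a spurious 5 mmHg difference.

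The model omits dropout, the diastolic trigger and lenvatinib interruption or reduction. It is illustrative only.

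**The case against.** **Small consequence.** The by-visit table is descriptive, and the SAP plans no between-arm test at any visit. Hypertension is assessed elsewhere: adverse events of clinical interest and time to first onset (SAP 5.6.3.11), and the worst-grade shift table and the listing of readings of at least 140 or 90 (SAP 5.6.5). SAP 8.1 includes all scheduled and unscheduled readings in worst-grade and shift analyses. A BP-triggered subject is already in the top grade of SAP Table 8. The primary endpoints, ORR at 24 weeks and the proportion with specified TEAEs, do not use visit means. All of this stands and limits the point to presentation of safety data.

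**Not necessarily high.** A reader might infer that these Day-15 pressures are high by construction, with a sawtooth of some 16 to 22 mmHg as in the simplest model. The documents do not support that. Selection is on an earlier reading; antihypertensives, and if needed lenvatinib interruption and reduction, come in between; subjects keep attending while controlled; and those recalled for proteinuria are not selected on pressure. Nothing pushes pulse, respiratory rate, temperature or weight upward. This objection stands against any claim about direction, but it does not rescue the rows: an unpredictable distortion is no easier to read.

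**Shells may handle it.** Table shells and dataset specifications are separate documents (SAP sections 9 and 11) and may already restrict the visits shown. That is possible, but the rule the SAP states has no such restriction.

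**Conclusion.** The point holds as a defect in a descriptive display. From Cycle 3, Day-15 vital-sign rows summarize a subset chosen by post-randomization toxicity; they are not comparable with Day-1 rows, nor between arms as randomized groups. This follows from the schedule and the SAP text and needs no assumption.

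The size does need assumptions. Under those listed, attenders differ from all subjects by about +16 to -10 mmHg in mean systolic pressure, with about zero at a 20 mmHg antihypertensive effect, and attenders are about 5 to 38% of subjects. A reader should not infer a known upward bias, nor that any conclusion on the primary endpoints is at risk. The change is worth making because it is specific, nearly free and concerns a key toxicity in a dose comparison.

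A related contradiction affects who is in these rows. Table 6 footnote e ends BP monitoring after 3 consecutive months at or below 150/95; protocol 9.4.2.2 and 9.5.1.4.4 end it after one 56-day cycle. The same two durations conflict for dipstick testing (footnote l against 9.4.2.3).

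**What to change.** In SAP 5.6.5 and 8.1, limit by-visit vital-sign statistics to visits required of all subjects: Baseline, Cycle 1 Day 1 and Day 15, Cycle 2 Day 1 and Day 15, Day 1 of each later cycle, and Off-Treatment. Keep the Day-15 readings from Cycle 3 onward in the worst-value shift tables and listings, or show them in a separate table with n by arm and a footnote saying how attenders were selected.

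The cost is about one sentence in the SAP and a visit filter in the table programs. No new data are needed and no reading is lost.

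Separately, the protocol sections on when BP and dipstick monitoring end must be reconciled, since they decide who attends Day 15. Which duration applies is for the sponsor to state.
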